Protocol: Pharmacokinetics of Advantage Arrest

Protocol version: 2016-11-08 NCT04184271 Document Date: 11/08/2016

Sponsor:	Advantage Silver Dental Arrest, LLC [name] United States
Investigator:	[name] University of Washington [name] United States Email: [contact] [contact]
Sub-investigators:	[name] University of Washington [contact]
	[name], PhD University of California, San Francisco [contact]
Research Site:	University of Washington Regional Clinical Dental Research Center [name] United States [contact]
Regulatory Monitor:	[name] Cooley Consulting, Inc. [name] United States [contact]

Purpose of the Study and Background

Objective: The purpose of this study is to characterize basic PK parameters (Cmax, $t_{1/2}$, AUC, and total urinary recovery) to contribute to evidence for the safety of Advantage Arrest, consistent with Guidance for Industry--Exposure--Response Relationships (April 2003). On a preliminary basis, we will also characterize the microbiome before and 24-hours after the topical treatment.

Background: The Sponsor/Investigator conducted a preliminary PK study in six adults (Vasquez et al., 2012) in which 38% diammine silver fluoride (silver diamine fluoride) was applied topically to three teeth in each subject and maximum serum concentration and time to maximum serum concentration were studied over four hours. Mean amount of the agent applied was 7.57 mg. Over the four-hour observation period the mean maximum serum concentrations were 1.86 umol/L for fluoride and 206 nmol/L for silver. These maximums were reached at 3 h and 2.5 h for fluoride and silver, respectively. Fluoride exposure was below the EPA oral reference dose. Silver exposure exceeded the EPA oral reference dose for cumulative daily exposure over a lifetime, but for occasional use was well below concentrations associated with toxicity. Nevertheless, the number of subjects was limited and the follow-up period too short to calculate the AUC. Although diammine silver fluoride is available in many countries, there are no other published PK studies to our knowledge.

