Baseline procedures: When informed consent has been obtained, age, race, gender, and ethnicity information will be collected at baseline along with a brief health history. A brief visual examination will be conducted to note any evidence of inflammatory or ulcerative changes to the gums or other oral tissues. Non-fluoride toothpaste will be used on the day of the baseline appointment through the 24-hour blood draw period. An 18 gauge sterile venous cannula will be placed in an upper extremity. An initial blood sample of 6 mL (one tube for serum collection) will be withdrawn using a fluoride free tube (BD Vacutainer with Clot Activator Plus Royal Blue Stopper). Subject will void for a baseline urine sample collection. Using a dental microbrush, dental plaque will be collected from the buccal surfaces of the upper posterior teeth and the microbrush inserted in a sampling tube and agitated.

Study intervention: Advantage Arrest, Aqueous Diamine Silver Fluoride [Ag(NH₃)]₂F, CAS RN 33040-28-7, 38.3% to 43.2% in purified water 5.0 - 5.9% (w/v) fluoride; 24.4 - 28.8% (w/v) silver, Silver Diamine Fluoride

Teeth will be brushed with a soft toothbrush to remove debris and dried with cotton prior to application. The specific procedure is that 5 mg (1 drop) of Advantage Arrest will be dispensed into a plastic dappen dish and all of the material will be applied to the facial cervical surfaces of 5 posterior teeth with an applicator. To calculate the amount of Advantage Arrest applied: the dappen dish with the initial amount of Advantage Arrest dispensed and applicator will be weighed before application and after application. The amount applied will be calculated as the difference in weights before and after application. The amount applied will be recorded. The teeth will remain isolated with cotton rolls for 3 minutes and then rinsed with water and high volume evacuation. Subjects will not eat for at least 2 h following application of the test agent.

Blood, urine and plaque sampling following intervention:

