Subjects will have blood samples of 6 mL withdrawn at 30 min, 1h, 2h, 3h, 4h, 6h, 8h, 12h and 24 hours. Urine will be collected for a 24-hour cumulative sample following application of the study intervention. Subjects will continue to collect urine in the original container until 12h and be provided instructions and a container to continue the urine collection to 24 hours. Subjects will remain at the research site through the 12 hour blood and urine collection and return for the 24-hour timepoint. A 24-hour plaque sample will be obtained in the same manner as the baseline sample.

Blood, urine and plaque sample processing:

Blood samples will be spun in a clinical centrifuge, the serum withdrawn, and then the serum will be frozen for later analysis. The total volume of urine at baseline, 12 and 24 hours will be recorded and a 10 mL aliquot will be taken of each sample and frozen for later analysis. Plaque samples will be placed in a receiving tube, the tube agitated, and the contents frozen for later analysis.

Sample Analysis: Serum and urine samples will be analyzed for F- by ion chromatography and Ag+ by ICPMS (Inductively coupled plasma mass spectrometry). Cmax, Tmax, Cmin (last measurable time point), $t_{1/2}$, and the AUC will be calculated from serum samples. Total amount recovered will be calculated from urine samples. Plaque will be analyzed by 16S ribosomal RNA profiling.

Data Analysis and Monitoring:

Subject disposition: The frequency and reason for subject withdrawal will be summarized.

Data Analysis and reporting: The PI and sub-investigators will be responsible for performing all analyses, creating the output for the analyses and disseminating results to the study team. The Principal Investigator and the rest of the study team will then review the results. The Principal Investigator will be responsible for drafting and preparing a final report of the study.

Data Storage and Confidentiality

The data will be stored on password protected computers in the Clinical Research Center at the UWMC and in a locked cabinet and on password protected computers at the Regional Clinical Dental Research Center at the University of Washington School of Dentistry. Only investigative personnel will have access. The data will be available for inspection by regulatory monitors and FDA.

Risk-Benefit Assessment

Risk Category: Greater than Minimal Risk

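### The preliminary before/24-h microbiome comparison is confounded by the study cleaning, and time since last brushing is neither set nor recorded at either plaque swab

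*Protocol*

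**What the plan says.** The protocol's Objective adds a secondary aim to the pharmacokinetic ones: "On a preliminary basis, we will also characterize the microbiome before and 24-hours after the topical treatment".

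Under Baseline procedures, the last step listed is the first plaque sample: "Using a dental microbrush, dental plaque will be collected from the buccal surfaces of the upper posterior teeth". The same paragraph holds the only oral-hygiene instruction in either document: "Non-fluoride toothpaste will be used on the day of the baseline appointment through the 24-hour blood draw period".

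Under Study intervention, the preparation step is: "Teeth will be brushed with a soft toothbrush to remove debris and dried with cotton prior to application". The agent is then "applied to the facial cervical surfaces of 5 posterior teeth with an applicator". After three minutes of cotton-roll isolation the teeth are "then rinsed with water and high volume evacuation".

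The section on sampling after the intervention says: "A 24-hour plaque sample will be obtained in the same manner as the baseline sample". Subjects stay on site to 12 h, leave, and come back at 24 h. Sample Analysis names 16S ribosomal RNA profiling as the assay. The SAP does not mention the microbiome and plans no statistical comparisons because the study has a single arm.

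**The concern.** A before/after comparison of plaque is informative about a product only if the two samples would have been comparable without it. Here the first swab is taken from plaque left undisturbed for an unknown time. The second comes from the same surfaces after a swab, a toothbrush, drying, the agent, a rinse and evacuation. Repeating the sampling technique matches the method and the site, but not the time since the surface was last cleaned.

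If composition depends on time since cleaning, a shift at 24 h could come from the toothbrush as easily as from the agent, and an absent shift could be two effects cancelling. At stake is what the preliminary aim can tell a later study. If brushing times are not collected, no later analysis can recover them.

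**Working it through.** No figure in the plan bears on this point, so there is nothing to reproduce. The check sets the protocol's steps in order and asks what the 24-h minus baseline difference contains.

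| Step | Source in protocol | Time since last brushing |
|---|---|---|
| Baseline swab, upper posterior buccal surfaces | Baseline procedures | Not set, not recorded |
| Brushing and drying | Study intervention | Reset, to the extent that the sampled teeth are brushed |
| Agent on 5 posterior teeth, arch not stated | Study intervention | – |
| Rinse and evacuation | Study intervention | – |
| On site to 12 h, then away | Sampling following intervention | Further brushing not barred |
| 24-h swab, same technique and sites | Sampling following intervention | Not set, not recorded |

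**What the difference contains.** For each subject write D = A + C + H + T, where
- A is the effect of the agent;
- C is the effect of the study cleaning and the regrowth after it;
- H is the effect of any difference in time since brushing between the two swabs;
- T is everything else that changes over the day, such as the toothpaste switch and the two hours without food.

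**A and C cannot be separated.** Both are present in every subject. Nobody receives the cleaning without the agent. The protocol describes no sham application, no separately sampled site that was cleaned but untreated, and no swab between cleaning and application. Only the sum A + C + T can be estimated, with H on top. This is so with 16 completers, with 20, or with more: a larger sample narrows the interval around the sum but does not split it.

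**H is avoidable.** At baseline the interval since brushing has no stated limit. At the second swab it is about 24 h if the study brushing was the last one and covered the sampled teeth. It is at most 24 − 12 = 12 h if the subject brushed after leaving the site at 12 h. The toothpaste rule runs through the 24-h blood draw and so presupposes ordinary brushing in that window. H therefore varies from subject to subject in an unrecorded way.

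**What the second sample is.** The protocol does not say which teeth are brushed or how completely plaque is removed. The 24-h sample is best regarded as a mixture of residual and regrown plaque in unknown proportion.

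**The case against.** The strongest reply is that the plan makes no claim that the product causes any change. The aim is preliminary and descriptive, with no hypothesis, endpoint or test. Brushing and drying are written under Study intervention, so a description of the treatment as delivered legitimately includes them. Any uncontrolled before/after study has this limit, and a sentence in the report would cover much of it. This stands. It limits the consequence to interpretation, and it is why the fix asks for the result to be reported as that of the whole procedure. It does not excuse H, which is not part of the treatment and can be largely removed by instruction.

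A reader might also infer more than the documents support:
- *That the 24-h plaque is wholly regrown and at most 24 h old.* This would require the soft brush and the swab to clear the sampled surfaces. The protocol does not say so, and residual plaque would be older.
- *That the brushing interval is mismatched in every subject.* It is unspecified, which is different. The two swabs are about 24 h apart, and a subject who brushes every morning could have similar intervals at both.
- *That complete confounding means a large distortion.* Cleaning and agent coincide in all subjects, but neither document has data on how composition changes after brushing.

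On practicality, baseline procedures begin after consent and no earlier visit is described, so an instruction for the day before needs earlier contact. That is a real cost but a manageable one. Subjects already call or email to schedule, and the toothpaste rule for the appointment day already implies instructions before the visit.

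**Conclusion.** The concern holds in a limited form. The microbiome comparison is confounded by cleaning in every subject, and time since brushing is uncontrolled and unrecorded at both swabs. As written, neither a shift nor its absence can be assigned to the agent. The size and direction of the distortion cannot be computed from the documents.

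The conclusion rests on two assumptions: that the study brushing reaches at least some of the sampled upper posterior surfaces, and that plaque composition depends to some degree on time since cleaning. It does not depend on complete plaque removal or on all subjects having unequal intervals.

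The pharmacokinetic objectives are untouched. A change is worth making because it is cheap and must be made before sampling, but it concerns a preliminary aim and does not threaten the study's main purpose.

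**What to change.** 1. At scheduling, with any consent needed obtained beforehand, instruct subjects to brush with non-fluoride toothpaste about 24 h before the baseline swab and then not to brush until it is taken.
2. Ask them likewise not to brush between the study cleaning and the 24-h swab.
3. Record the time of last brushing at both swabs.
4. In the report, describe the contrast as that of the whole treatment procedure, cleaning included, and state that it cannot be attributed to the agent alone.

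Steps 1 and 2 bring both intervals to about 24 h and so remove most of H. They leave A, C and T together; matching does not replace a control.

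The cost is two intervals of about 24 h without brushing, a toothpaste rule that starts one day earlier, earlier contact with subjects, and one recorded time per swab.

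A swab of brushed but untreated teeth is not required. It adds sampling and sequencing cost, and those teeth may be exposed to the agent through saliva, in which case part of the agent's effect would be subtracted as if it were cleaning.

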Assumptions: This is a topical agent where the active ingredients are applied to the teeth and eventually swallowed and may be absorbed through the GI tract or excreted. Minimal amounts are absorbed through the oral mucosa. Serum concentrations of silver and fluoride will be be proportional to the dose of silver and fluoride administered topically to the teeth as part of Advantage Arrest. The total urinary recovery of fluoride, adjusted for baseline levels, will be calculated to estimate the minimum amount absorbed in each patient following application of the varnish. As biliary excretion is the principle route of elimination of silver (Lansdown et al., 2010), it is unlikely that significant amounts of silver will be recovered in the urine.

Criteria for Subject Selection

Number of subjects: There will be up to 20 healthy adult subjects enrolled in the study with the goal of at least 16 subjects to complete the study.

Gender of subjects: The subjects will be approximately half male and half female. **Age of subjects:** Subjects must be 18 years of age or older.

Racial and Ethnic Origin: In a small study it is not possible to fully represent the racial/ethnic distribution of the region or US. The investigator will attempt to recruit a racial/ethnic diverse population.

Inclusion criteria: Subjects will have at least 20 teeth. Subjects will be healthy and taking no prescription or OTC medications, including topical fluoride gels or rinses. Healthy status will be determined by self-reported medical history by the attending clinician.

Exclusion criteria: Subjects will be excluded if they have oral mucositis or any ulcerative lesions or hypersensitivity to silver or fluoride. Subjects who are pregnant, breastfeeding, or weigh less than 110 pounds will not be eligible to participate.

Methods and Procedures

Design of the Study and Minimization of Bias: Open label exposure--response study.

Randomization: Not applicable

Blinding: Not applicable

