Analysis Plan: Pharmacokinetics of Advantage Arrest

NCT04184271

Document Date: 07/30/2020

For the pharmacokinetic analysis, baseline serum fluoride and silver concentrations will be assessed and when appropriate, subtracted from other timed serum concentrations to adjust for baseline levels.

Pharmacokinetic analysis will be performed using Phoenix WinNonlin (Certara).

- The time to peak concentration (T_{max}), observed and baseline-corrected peak concentrations (C_{max}), and observed 24-h concentration (C_{24 h}) will be reported.
- The elimination rate constant (k_{elim}) will be determined by nonlinear regression with a minimum of 3 time points with decreasing concentrations over time observed after the peak concentration.
- Half-life (t_{1/2}) will be calculated as ln(2)/k_{elim}.
- Area under the curve (AUC): The 24-hour AUC (AUC_{0-24 hr}) will be calculated using a log-linear trapezoidal rule of baseline-corrected serum concentrations from time = 0 to 24 h. The AUC_{0-∞} will be calculated using a log-linear trapezoidal rule of baseline-corrected serum concentrations and extrapolated to infinite time by C_{24hour}/k_{elim}, where C_{24hour} is the 24 hour concentration.
- The percent extrapolated AUC will be calculated as $(AUC_{0-\infty} AUC_{0-24 \text{ hr}})/AUC_{0-\infty} \times 100$.
- The total urinary recovery of fluoride and silver will be determined by multiplying the concentration measured in the urine collected over 24 hours by the total volume of urine collected over 24 hours.

Statistical analysis will be performed using Excel to calculate the mean \pm standard deviation for the pharmacokinetic parameters. No statistical comparisons will be made as it is a single arm study.

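### The SAP neither summarises nor uses the weighed amount applied to each subject, so dose differences are left unadjusted in Cmax, AUC and urinary recovery

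*Protocol*

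**What the plan says.** In the protocol's Study intervention paragraph (Methods and Procedures), each subject is assigned the same nominal quantity: "5 mg (1 drop) of Advantage Arrest will be dispensed into a plastic dappen dish and all of the material will be applied" to five posterior teeth. The protocol does not rely on that nominal figure. The dish and applicator are weighed before and after: "The amount applied will be calculated as the difference in weights before and after application". It adds: "The amount applied will be recorded". After 3 minutes the teeth are rinsed with water and high volume evacuation.

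Under Assumptions, the protocol takes serum silver and fluoride to "be proportional to the dose of silver and fluoride administered topically to the teeth as part of Advantage Arrest". The same paragraph wants urinary fluoride recovery, adjusted for baseline, as an estimate of the least amount each patient absorbed.

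Under Background, the preliminary study in six adults is described: "Mean amount of the agent applied was 7.57 mg", on three teeth each, and "the mean maximum serum concentrations were 1.86 umol/L for fluoride and 206 nmol/L for silver".

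The SAP lists Tmax, observed and baseline-corrected Cmax, C24h, k_elim, half-life, AUC0-24, AUC0-∞, percent extrapolated, and urinary recovery as concentration times volume. It closes with: "Statistical analysis will be performed using Excel to calculate the mean" and standard deviation of these parameters, with no statistical comparisons. The amount applied appears nowhere in it.

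**The concern.** The plan measures a quantity that it takes to drive serum concentration, and then does not use it. A raw mean and SD of Cmax or AUC combines how much product went on the teeth with how it was absorbed and eliminated, and the report as planned would give a reader no means of separating the two. It would not even state the dose at which the exposures were observed.

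Two readings are at stake. First, the protocol says that it knows of no other published PK study, so readers will naturally set the new Cmax beside the preliminary one. A lower value caused only by a smaller amount could be taken as lower systemic exposure. Second, fluoride recovery given only as an amount cannot be related to what was applied. The proportionality assumption would also go unexamined, although the data for a descriptive look are collected.

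**Working it through.** The plan states no figure on this point, so there is none to reproduce. The check has three parts.

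**1. Does any SAP parameter contain a dose term?** Cmax, C24h, AUC0-24, AUC0-∞ and urinary recovery scale with dose under proportionality, and none is divided by it. Tmax, k_elim and half-life do not depend on dose under linear kinetics, and percent extrapolated is a ratio of AUCs, so the omission does not affect these four.

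**2. Difference from the preliminary Cmax due to dose alone.** Inputs (Protocol, Background and Study intervention): mean amount 7.57 mg; mean Cmax 1.86 umol/L fluoride and 206 nmol/L silver; nominal amount now 5 mg.

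- Ratio of amounts: 5 / 7.57 = 0.66, a reduction of 34%.
- Cmax per mg, as a ratio of means: fluoride 1.86 / 7.57 = 0.246 umol/L per mg; silver 206 / 7.57 = 27.2 nmol/L per mg.
- Expected Cmax at 5 mg: fluoride 1.86 × 0.66 = 1.23 umol/L; silver 206 × 0.66 = 136 nmol/L.

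The fluoride figure is approximate. Endogenous fluoride does not scale with dose, and the documents do not say whether the preliminary Cmax was baseline-corrected.

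**3. Share of within-study variance due to dose.** The documents give no CV for the amount applied or for PK at a fixed dose, so both are assumed. With exposure = amount × (exposure per mg), and the two factors independent:

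- Raw CV² = (1 + CVd²)(1 + CVb²) − 1
- Dose share = CVd² / raw CV²

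Here CVd is the CV of the amount and CVb is the CV of exposure per mg.

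| CVd | Raw CV, CVb 30% | Dose share | Raw CV, CVb 50% | Dose share |
|---|---|---|---|---|
| 5% | 30.5% | 2.7% | 50.3% | 1.0% |
| 10% | 31.8% | 9.9% | 51.2% | 3.8% |
| 20% | 36.6% | 30% | 54.8% | 13% |
| 30% | 43.4% | 48% | 60.2% | 25% |

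Example: with CVd 20% and CVb 30%, raw CV² = 1.04 × 1.09 − 1 = 0.1336, and the share is 0.04 / 0.1336 = 30%.

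**What normalising would need.** Values per mg of product need only the weights. Values per mg of ion need more. Strength is stated as a w/v range, 5.0 to 5.9% fluoride and 24.4 to 28.8% silver (5.9 / 5.0 = 28.8 / 24.4 = 1.18, about 18% wide), and a weight must be converted to a volume. With an assumed density of 1.0 to 1.3 g/mL, 5 mg of product holds between 5 × 0.050 / 1.3 = 0.19 mg and 5 × 0.059 / 1.0 = 0.295 mg of fluoride. That range is too wide for a percentage recovered unless lot strength and density are known.

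**The case against.** The strongest reply is that a reader might infer that the endpoints cannot be compared at all, and the documents do not support that. The weights are recorded for each subject, so normalised values can be derived at any time. Every subject has the same nominal amount, so raw values are comparable to the extent that delivery is uniform, and nothing in the documents shows that it is not. This stands: the gap is in the planned analysis and not in the data.

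Next, only Cmax has a counterpart in the preliminary study. Its follow-up was too short for an AUC, and the documents report no urinary recovery from it. Even a Cmax per mg would compare three treated teeth with five, and 4 hours of sampling with 24. The protocol does not make this comparison an objective, and the SAP plans none. This stands too, and limits the one-third figure to a caution about reading the two Cmax values side by side.

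A reader might also infer that dose is the main source of between-subject variation. Neither document ranks the sources or gives a dose CV, and at a dose CV of 5% to 10% the share is small.

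Lastly, the protocol defines fluoride recovery as an amount, so a percentage is an addition and not a correction of a departure. That is right, but it does not answer the bare omission: a weighed dose that is never reported. The additions are descriptive, so the absence of statistical comparisons is no bar. Specifying them in the SAP avoids choosing a normalisation after the results are seen.

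**Conclusion.** The concern holds as a gap between protocol and SAP: the amount applied is weighed, recorded and assumed to drive serum levels, yet is neither summarised nor used. The planned raw parameters remain valid descriptions and serve the stated objective, but dose differences in them are left unadjusted.

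For Cmax against the preliminary study, the size is about one third, on the assumptions of exact proportionality and delivery of the nominal 5 mg. Within the study it is unknown. It runs from about 1% to 10% of variance at a dose CV of 5% to 10%, to about 13% to 48% at 20% to 30%, with assumed other CVs of 30% to 50%, independence, and a denominator without weighing error. The omission itself is certain; its within-study importance is not. The change should be made because it costs little and widens what the study can report.

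**What to change.** Keep all raw values and add to the SAP:

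- (a) mean, SD and range of mg of product applied;
- (b) baseline-corrected Cmax, AUC0-24 and AUC0-∞ per mg of product applied, and per mg of fluoride or silver only if lot strength and density are available;
- (c) urinary fluoride recovery as a percentage of fluoride applied, under the same condition. The numerator must be baseline-adjusted, which the protocol's Assumptions call for and the SAP's recovery formula omits; otherwise background fluoride counts as absorbed product. The SAP should say how the baseline void is used for this;
- (d) a descriptive plot of baseline-corrected Cmax and AUC0-24 against amount applied, with no test.

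State also that the amount applied is an upper bound on the amount available for absorption, because the teeth are rinsed with high volume evacuation.

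The cost is SAP wording and a few derived columns. Items (a), (d) and the per-mg-product part of (b) use only data that the protocol already collects. The ion-based values also need lot strength and density. The small downside is that weighing error enters the normalised values, which is a further reason to show the raw values beside them.
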